5.2 Missing Data

No imputations will be performed, except as noted for the sensitivity analysis for the primary endpoint as described in Table 1 ([Section 5.1.4](#)). In all other cases, missing data will be excluded and variables will be analyzed using the available observed data.

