10.4.1 Analyses of Study Endpoints

For the primary endpoint, the proportion of CS patients who are at least somewhat satisfied with their overall symptom control at 6 months, a point estimate and the corresponding 95% CLs will be calculated. Secondarily, a point estimate and corresponding 95% CLs will be calculated for the proportion of CS patients who are very satisfied with their overall symptom control at 6 months. The 95% CLs will be unadjusted and based on the assumption of approximate normal distribution. Missing data will not be imputed in the main analysis of the primary endpoint. As a sensitivity analysis, a patient with a missing response at 6 months will be imputed as a non-responder. This approach corresponds to non-responder imputation.

In addition to the point estimates and 95% CLs for the primary endpoint, the frequency distribution of the categorical responses, on a 5-point Likert scale, to patient satisfaction with overall symptom control at 6 months will be presented. The patient satisfaction measure will also be summarized as an ordinal variable with a value of 1 corresponding to “very dissatisfied” up to 5 corresponding to “very satisfied”.

All the secondary endpoints correspond to proportions and will be summarized through point estimates and 95% CLs, as described above for the primary endpoint. Frequency distributions of the categorical responses and summary statistics of the corresponding ordinal values of the categories will be presented. The handling of patients with a response of “not applicable” to patient satisfaction with CS-related diarrhea control or patient satisfaction with CS-related flushing control in the analysis will be described in the SAP.

The 4 WPAI-SHP scores at Baseline and month 6 will be summarized, as well as the change from Baseline to month 6.

The incidences of at least 1 CS-related hospitalization, at least 1 CS-related ER visit, and mortality after Baseline will be calculated at each 6-month interval. Kaplan-Meier estimates of each time-to-event variable, including quartiles, medians, and their corresponding 95% CLs, will be presented. The association or relationship between the primary endpoint and each long-term health outcome will be evaluated through descriptive statistics and the use of statistical models, as appropriate. Any statistical models that will be used and the appropriateness and/or limitations of their use will be described in the SAP.

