2 STUDY DESIGN AND OBJECTIVES

2.1 Study Design

This observational, noninterventional, single-arm study will include adult patients with CS who are initiating XERMELO as a new treatment. A minimum of 643 patients are expected to enroll.

A specialty pharmacy tasked with distributing XERMELO to patients will be responsible for the identification and recruitment of patients, and all eligible patients who are initiating treatment with XERMELO will be invited to participate in this study. Patients who enroll will be asked to complete up to 7 longitudinal, web-based surveys, including a Baseline assessment at enrollment, and a Follow-up survey every 6 months for up to 3 years. The Baseline questionnaire may be completed any time within a 30-day window following the electronic mail invitation to a patient to participate in the survey. The Follow-up surveys at 6-month intervals may be completed at any time within a \pm 14-day window.

Prescription fill data, type of insurance, and reasons for discontinuation, including mortality, will be collected directly from the specialty pharmacy using a process that is still being determined and will be described in a separate document.

A full description of the study design is found in the study protocol dated 19 May 2017 (Lexicon Pharmaceuticals, Inc.).

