2.4 Sample Size Determination

The sample size was derived by satisfying design assumptions for the primary study endpoint of the proportion of patients with CS who are satisfied with their overall symptom control, 6 months after initiating treatment with telotristat ethyl (XERMELO). Of specific interest is the proportion of patients with CS who are at least somewhat satisfied with their control of CS at 6 months, defined as those patients with a response of either "very satisfied" or "somewhat satisfied". This proportion will be estimated as x/n , where x is the number of patients in the study who are either "Very satisfied" or "Somewhat satisfied", and n is the number of patients with a non-missing response for the primary endpoint. Two-sided 95% confidence limits (CLs) will be calculated for this proportion using normal approximation. The true proportion may be approximately 50%; hence, an expected proportion of 50% was used in the sample size calculation as it requires the largest n . It is desired for the proportion to be known with a precision, ω , of 5%, that is, for the CLs to be $(x/n) \pm \omega$. Based on the expected proportion of 50% and the precision requirement of 5%, $n = 385$ patients are needed to have a non-missing response for the primary endpoint. Assuming that 40% of the patients who participate in the study will drop out prior to the 6-month survey, then a minimum of $N = 643$ patients, with CS who initiate treatment with XERMELO, should be entered into the study.

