5.1.4 Primary and Secondary Endpoint Analyses

Responses to questionnaire items related to the primary and secondary endpoints will be summarized as categorical variables, as described in [Section 5.1.1](#). Items having ordinal response scales consisting of at least 5 categories will also be summarized as ordinal variables. Estimates of proportions for all primary and secondary endpoints at the initial 6-month Follow-up will be accompanied by 2-sided 95% CLs based on the normal distribution approximation.

For estimation of the proportions for the primary and secondary endpoints, patients will be categorized based on their responses to the corresponding questionnaire items as described in Table 1. Responses of "Not applicable" will be excluded from the denominator for computation of each proportion. Missing data will not be imputed, with the exception of a sensitivity analysis on the primary endpoint, whereby a patient with a missing response will be imputed as a non-responder (ie, neither "Very satisfied" nor "Somewhat satisfied"). Some endpoints will have supplemental/sensitivity analyses in addition to the main analysis, and specifications for those analyses are also shown in Table 1.

In addition to the proportions of patients reporting reduction from Baseline in the 4 domains of the WPAI-SHP, domain scores will be summarized at Baseline and at the initial 6-month Follow-up. The change in score for each domain over this 6-month interval will also be summarized as a continuous variable.

Table 1. Primary and Secondary Endpoint Definitions

	Definition for Main Analysis	Definition for Supplemental Analyses
Primary Endpoint (proportion of patients at 6 months after initiating treatment with XERMELO)		
Satisfaction with overall control of CS symptoms	“Very satisfied” or “Somewhat satisfied”	
 “Very satisfied” only [REDACTED]
Secondary Endpoints (proportions of patients at 6 months after initiating treatment with XERMELO)		
Satisfaction with control of CS-related diarrhea	“Very satisfied” or “Somewhat satisfied”	“Very satisfied” only
Satisfaction with control of CS-related flushing	“Very satisfied” or “Somewhat satisfied”	“Very satisfied” only
Reduction in rescue SSA use	“Less frequent”	N/A
Reduction in dose of long-acting SSAs	“Decreased”	N/A
Reduction in frequency of long-acting SSA injection	“Decreased”	N/A

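### Diarrhea satisfaction, flushing satisfaction and PGIC have no missing-data sensitivity analysis despite 40% planned loss before month 6, and the denominator of the primary non-responder analysis is not stated

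*SAP*

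**What the plan says.** - **Planned loss.** SAP 2.4 sizes the study "Assuming that 40% of the patients who participate in the study will drop out prior to the 6-month survey", and SAP 2.1 gives the enrollment target: "A minimum of 643 patients are expected to enroll".
- **Missing data.** SAP 5.1.4: "Missing data will not be imputed, with the exception of a sensitivity analysis on the primary endpoint". SAP 5.2 repeats this ("No imputations will be performed, except as noted for the sensitivity analysis for the primary endpoint") and has everything else analyzed on observed data.
- **Supplemental analyses.** In SAP Table 1 the supplemental entries for diarrhea satisfaction, flushing satisfaction and PGIC are legible. They narrow the definition of response (top satisfaction category only; top two improvement categories only) and do not deal with missing responses. Part of the primary endpoint's supplemental entry is redacted.
- **Analysis population.** SAP 5.1.2 and Protocol 10.2 include enrolled, consenting patients with data on at least one primary or secondary endpoint. SAP 2.3 and Protocol 10.3.1 place all of these endpoints at 6 months.
- **Leaving the study.** Protocol 5.1.1 makes participation depend on continued XERMELO use, and SAP 3.2.7 terminates patients who stop it. After Baseline, satisfaction and PGIC are asked only at month 6 (SAP 3.2.3 and 3.2.4; Protocol Appendix A).
- **Not applicable answers.** The diarrhea and flushing items offer this option (SAP 3.2.3), and SAP 5.1.4 removes such answers from the denominator.

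**The concern.** A patient who leaves before month 6 loses every month-6 item at once, and no later survey asks these questions again. The loss is unlikely to be unrelated to the outcome: stopping the drug ends participation, and Protocol 3.2 records the sponsor's own assumption that satisfied patients will stay on treatment. If that is right, responders over-represent satisfied patients and the available-case proportions are probably too high. The direction is an inference from the documents, and the size is unknown.

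Carcinoid syndrome diarrhea is the drug's indication, so diarrhea satisfaction is likely to be quoted beside the primary result. The planned confidence limits describe sampling error among responders and say nothing about the missing 40%. The plan already accepts the remedy in principle, since it includes a non-responder analysis for the primary endpoint, but no legible text gives that analysis a denominator.

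**Working it through.** **Inputs.** From SAP 2.4: two-sided 95% limits by normal approximation, an expected proportion of 50%, a half-width of 5 points, and 40% dropout. From SAP 2.1: 643 enrolled. The documents give no expected proportions for the secondary endpoints, so the observed values below are assumptions.

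**1. Reproduce the plan's sample size.**
n = z²p(1−p)/w² = 1.96² × 0.25 / 0.05² = 384.16, rounded up to 385, as stated.
N = 385 / 0.60 = 641.7, rounded up to 642, against 643 stated. One patient is immaterial.

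**2. Planned missing at month 6.**
643 − 385 = 258, and 258/643 = 40.1%.

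**3. Bounds on a secondary proportion,** with all 643 in the denominator and no Not applicable answers.
Lower (all missing are non-responders): 385p/643 = 0.599p.
Upper (all missing are responders): (385p + 258)/643.

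| Assumed p in responders | Planned 95% CL (n = 385) | Lower bound | Upper bound |
|---|---|---|---|
| 50% | 45.0 to 55.0% | 29.9% | 70.1% |
| 60% | 55.1 to 64.9% | 35.9% | 76.0% |
| 70% | 65.4 to 74.6% | 41.9% | 82.0% |
| 80% | 76.0 to 84.0% | 47.9% | 88.0% |

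The bounds are always 258/643 = 40.1 points apart, while the planned interval is at most 10 points wide.

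**4. Dependence on the dropout rate.** The lower bound is p(1 − d). An assumed 70% becomes 63% at 10% loss, 56% at 20%, 49% at 30%, 42% at 40% and 35% at 50%.

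**5. Diarrhea and flushing.** Not applicable answers shrink the denominator. As an illustration, Protocol 3.1 puts diarrhea at roughly 75% of patients with the syndrome. Then n = 0.75 × 385 ≈ 289, and the half-width at 50% is 1.96 × √(0.25/289) = 5.8 points, so the 5-point precision no longer holds. If the same share applies to missing patients, the lower bound is still 0.599p (288.75/482.25 = 0.599). If it differs, the ratio changes.

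**6. Who the primary non-responder analysis reaches.** An early leaver has no month-6 data. Taken literally, SAP 5.1.2 excludes that patient, and the imputation would then cover only analyzed patients who skipped the primary item. The figures in step 3 need an all-enrolled denominator, which no legible text states. SAP 4.1.2 summarizes Baseline burden for all 643 patients, so the population definition may not be meant literally everywhere.

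**The case against.** **A protocol–SAP contradiction.** A reader might infer one from Protocol 10.4.1: "All the secondary endpoints correspond to proportions and will be summarized through point estimates and 95% CLs, as described above for the primary endpoint". The non-responder analysis stands in the text above that sentence. But the phrase attaches to point estimates and confidence limits, and the protocol synopsis makes the same statement where the primary-endpoint text mentions no imputation at all. Protocol 10.4.1 also ties its missing-data rule to the primary endpoint. The documents agree with each other.

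**A protected primary endpoint.** A reader might also infer that the primary result has a conservative companion figure that the secondary results lack. Step 6 shows that this contrast is not established. The redacted part of Table 1 may settle the denominator, but the legible text does not.

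**The information is already there.** SAP 5.1.3.1 tabulates completed questionnaires, discontinuations and reasons, and response frequencies are reported. For PGIC, which has no stated Not applicable option, anyone can divide the responder count by the number enrolled. This stands for PGIC: what is missing there is a prespecified row, not the data. For diarrhea and flushing the reader would also need to know how many of the missing had the symptom.

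**Deliberate choice in a descriptive study.** Restricting a missing-data sensitivity analysis to the primary endpoint is disclosed and common, and no error rate is at stake. This limits the weight of the point but does not remove it, given a planned loss of 40% that is probably related to the outcome.

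**Conclusion.** The point holds as a low-severity, inexpensive improvement. Three secondary endpoints are estimated from month-6 responders alone, with no missing-data sensitivity analysis, under the plan's own assumption of 40% loss. The same population definition leaves it unclear whether the primary non-responder analysis counts early leavers.

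At the planned numbers the lower bound sits 20 points below an assumed 50% (50 − 29.9) and 28 points below an assumed 70% (70 − 41.9). These figures assume 385 of 643 responding, an all-enrolled denominator and no Not applicable answers. They mark an extreme and should not be read as the expected bias.

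**What to change.** In SAP 5.1.4, SAP 5.2 and the supplemental column of Table 1:

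1. State that the non-responder sensitivity analysis uses all enrolled patients as its denominator, for the primary endpoint as well, whatever the definition in SAP 5.1.2.
2. Extend it to PGIC, diarrhea satisfaction and flushing satisfaction, labeled as a conservative lower bound.
3. For diarrhea and flushing, keep the main-analysis rule that a month-6 Not applicable answer is excluded. Use the Baseline answer to decide applicability only when the month-6 response is missing. A patient whose symptom has resolved is then not scored as a failure, and a patient with a real month-6 answer is not dropped. The text should also say what happens when the Baseline answer is missing too.

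The cost is a few extra sensitivity rows from data already collected, the applicability rule to be written and programmed, and a lower companion figure beside each estimate. The main analyses do not change.

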5.3 Quality Control

Per RTI-HS' standard operating procedure on analytic programming and quality control (QC), all analysis programs, whether used for creating analysis datasets or outputs (eg, table or listings), will undergo QC review prior to delivery to Lexicon. The exact method of QC to be performed is determined by the lead statistician and/or project director. Methods of QC include 100% independent programming, spot checking, and code review. For this study, a mix of QC methods has been budgeted. Specifically, 100% independent QC programming via SAS PROC COMPARE will be employed to review all analytic datasets. For tables, a mix of spot checking and independent QC programming will be implemented depending on the type and complexity of the table. For data listings, code review by an

independent programmer will be used. Regardless of the level of QC, all outputs will be checked for formatting and consistency.

Quality control will be documented in detail in a separate document and, if requested, can be delivered to Lexicon at the end of the study.

